5. PARTICIPANT ELIGIBILITY CRITERIA

5.1. Inclusion Criteria

- Referred for radical radiotherapy at the Robert White Radiotherapy Centre (RWRC)
- Histological or radiological diagnosis of cancer, or appropriate referral for benign condition
- Provision of informed consent to participate.

5.2. Exclusion Criteria

- Under 18 years old
- Patients who are unable to understand the study information or unable to complete questionnaires or the consultation, for example unable to speak English fluently.
- The documentation of an ongoing psychiatric condition in the patients' medical notes to which the researchers have access.
- Is participating in another patient-reported outcome investigation that may interfere with this study.
- Referred for palliative or emergency radiotherapy treatment.

5.3. Withdrawal Criteria

The patient at any point can ask to be withdrawn from the trial without an explanation or reason. Any patient results and questionnaires will be retained in line with Trust policy, and the quality of care they receive will not be affected.

6. TRIAL PROCEDURES

This section describes conduct of the study in chronological order, detailing the procedures for data collection at each of the time points.

Table 2: Tabulated Study Schedule

A tabulated study schedule to illustrate all data collection at each time point of the study.

TIMEPOINT	Baseline	Week 2 (before RT)	End of Study (before RT)
ENROLMENT:			
Eligibility screen	Х		
Informed consent	Х		
Baseline characteristics	Х		
Baseline socio- demographics	х		
Randomisation	Х		
INTERVENTION:			
Physicist consultation		Х	
ASSESSMENTS:			
Health literacy	Х		
STAIS6 Questionnaire	Х	Х	х
EQ-5D-5L	Х	Х	Х
Information & communication needs	х		х
Technical Satisfaction Questionnaire	х	Х	Х
Questions about Medical Physicist consultation			х

6.1. Recruitment

Table 3: Summary of recruitment tas	sks
-------------------------------------	-----

Recruitment Process	Detail	Responsible staff
Participant identification	Referral for radiotherapy will indicate patients who are having radical treatment at Dorchester.	Radiotherapy Bookings
Patient invitation	Invite letter and patient information sheet (PIS) with CT appointment letter, printed and posted.	Radiotherapy Bookings

6.1.1. Participant identification & invitation

Participants will be identified by radiotherapy staff already involved in their routine care (and therefore have authorised access to their identifiable information). Identification will occur when the referral for radiotherapy treatment is received from the Consultant Oncologist (or other entitled member of staff) by radiotherapy bookings staff in the Mosaiq Oncology Information System (OIS). The referral contains the required information to identify patients having radical radiotherapy at Dorchester. These patients will receive an invitation to the study (comprising the patient information sheet) with their CT appointment letter which is printed and posted to them. A record will be kept of patients who receive the invitation, and patients who decline to participate will be recorded (along with any reason if given) to identify recruitment problems as early as possible. The primary mechanism for recording recruitment will be the clinical trials label/alert available in Mosaiq.

Providing the patient information sheet (PIS) with the patient CT appointment letter ensures appropriate time to consider the information. The minimum period of time required (if the above process is not followed) is 24 hours. It will be documented in the OIS that the patient has had been provided with the PIS and had time to consider participation.

6.1.2. Screening

Confirmation of eligibility against the inclusion and exclusion criteria will be performed by the PI or delegated member of the research team when a patient notifies the trial team they would like to participate (before the routine CT appointment), or otherwise before patient consent. If the patient has consented and found to be ineligible the PI will contact the patient to inform them they won't be able to participate in the trial. Eligibility will be determined by examining the patients' medical record (EPR & Mosaiq).

6.1.3. Payment

It is not expected that any reimbursement for additional visits will be required as the trial intervention and data collection will occur during routine outpatient visits to the radiotherapy department.

6.2. Baseline visit

6.2.1. Consent

At the routine CT appointment of patients who received the study invitation and participant information sheet, the patient will be approached by the CI or delegated member of the research team to review the study information and discuss their participation in the trial, unless they have already contacted the study team to confirm/decline involvement. The right of a participant to refuse participation without giving reasons will be respected.

Participants will have been provided with contact details to obtain further information about the trial via the participant information sheet. This will be the dedicated study email address. This will be provided again at consent as required.

Potentially eligible patients who express willingness to participate will be asked to provide consent in accordance with Good Clinical Practice. The consent process will involve a full explanation of the trial given by the person taking consent. The person responsible for taking consent will be trained in GCP and Informed Consent. Patients will be advised that they are under no obligation to take part and that their ongoing care will be unaffected if they choose not to take part. Patients who choose not to take part will be asked to provide a reason for declining but will be told that they do not have to give a reason if they wish not to. Patients will also be advised that they are free to withdraw from the trial at any time and that doing so will not affect their ongoing care. Following this discussion, patients who are willing to participate will be asked to complete, sign and date the trial consent form, which will also be signed and dated by the person obtaining consent.

The CI is responsible for obtaining consent but may delegate these duties appropriately to other members of the research team. Such delegation will be captured on a site-specific site delegation log. Any person obtaining written informed consent must have current GCP training and have received trial-specific training from the trial team. No trial information will be gathered, or intervention carried out, prior to taking consent from the patient.

A copy of the signed Informed Consent form will be given to the participant. The original signed form will be retained in the Investigator Site File and a copy placed in the patient's hospital notes. Note that any new information that arises during the trial that may affect participants' willingness to take part will be reviewed by the TMG. If necessary, this information will be communicated to all participants, and they will be asked to re-confirm consent in light of the new information.

Patients who are found to be ineligible or who are unwilling to participate will be managed as per usual care. Reasons for non-participation (where given) will be recorded by the research team.

Participant ongoing consent will be confirmed on the first and last days of treatment (through asking "are you willing to continue in this study?"), including assessment of capacity to continue, and documented in their medical record.

Following any amendments to this protocol, the appropriate patients will be reconsented.

6.2.1.1. Remote / telephone consent

Due to the cross-site nature of this study, it is feasible that an appropriately delegated member of the research team is not available to obtain participant consent. Alternatively, the participant might require further time to consider the study information. In these circumstances, if the participant wishes to join the study:

- The participant will go home with a copy of the PIS and the baseline questionnaire
- A member of the research team will contact the participant via telephone to discuss the study and obtain consent.
- Once consent has been obtained, the participant will complete the baseline questionnaire and bring with them to their first radiotherapy appointment (to maintain required timelines for data collection outlined below).

Telephone consent will be undertaken in line with the following:

- A telephone consent form will be used.
- The participant will be asked to complete a written Consent form at their next visit.
- The participant will receive copies of all consent forms, to include the telephone consent form.

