6.2.2. Baseline data

After eligibility has been confirmed and written consent obtained, and prior to randomisation, patients will be provided with a baseline questionnaire packet to be completed, and a member of the research team will complete the baseline case report form (CRF).

- Sociodemographic information collected from either medical records or selfreported by the participant.
 - Contact details, and preferred method of contact (to facilitate sending of appointments and questionnaire reminders).
 - o Year of birth
 - o Gender
 - Education level
 - Marital status
 - Employment status
 - Whether the participant deems English to be their 'first' or 'second' language
 - Clinical information collected from medical records
 - Area/site of treatment
 - Number of radiotherapy treatments (fractions) referred.
 - Has the participant had previous radiotherapy?
 - Has the participant been scanned with particular motion management, e.g. deep inspiration breath hold (DIBH)?
- Patient-reported anxiety STAIS6 questionnaire
- Health literacy assessment
- EQ-5D-5L questionnaire
- Information and communication questions
- Technical satisfaction questions

Ideally the participant-reported data will be collected on the day of consent, however it is acknowledged this may not be possible in all cases. This must be completed within 1 week of the CT appointment, either by post or electronically.

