6.3. Randomisation

Following completion of baseline information collection, a member of the research team will randomise the participant to one of the two treatment arms: physicist consultation or standard of care.

Patients will be randomised in order to minimise systematic bias, using a secure web-based system Sealed Envelope (https://www.sealedenvelope.com/simple- randomiser/v1/trials/rapport), certified as meeting ISO/IEC 27001 standards and the NHS England Data Security and Protection Toolkit.

Participants will be allocated to intervention group or to the control group in a 1:1 ratio. Randomisation will be stratified by gender. This is a surrogate for treatment site: the most common radiotherapy treatment sites (particularly at RWRC) are breast and prostate cancer. However, to ensure approximately equal distribution of treatment sites in each arm and avoid problems of low numbers of less common treatment sites, gender has been chosen has the stratification criteria. It is acknowledged that with the low sample size required in this study, distribution is likely still to be unequal but there is little evidence that the primary outcome varies by gender.

Upon randomisation, each participant will be assigned a unique Trial Number which will be used as the principal identifier on trial data collection forms and questionnaires. The research team member will disclose the allocation to the participant and will ensure the allocation is followed as described below.

6.4. **Provision of Treatment**

Following allocation, the participant will be informed of which trial arm they have been randomised to. Where required, the consultation will be booked by the PI or delegate and the patient informed what time this will be (as it will not be on their routine appointment list given at the CT appointment). If possible, a reminder will be sent via the DoctorDoctor service.

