8.2.2. Primary outcome

The primary outcome is the Spielberg state-trait anxiety index (STAI). Questionnaires that were not completed in the required timeframes will be treated as missing data:

- Baseline within 1 week of CT appointment
- Start of treatment on day of treatment
- End of treatment on day of treatment

Anxiety scores will be compared at each time point between the two groups for a statistically significant difference. The 2nd and 3rd timepoints will use baseline-corrected anxiety scores. Some additional analyses (including sensitivity analyses) on the primary outcome will also be conducted:

- a. The effectiveness of the intervention may vary across different subgroups of patients (e.g. age, education level). Therefore, supplementary statistical analyses are proposed in which it is tested if there is a statistical interaction between socio-demographic data and the primary outcome. This will include health literacy level measured at baseline.
- b. Any baseline variables that appear, by chance, to differ between the groups will be added in as covariates.
- c. Whether or not the patient has had previous radiotherapy will be added as a covariate.
- d. Longitudinal analysis of anxiety scores at all three time points to assess variation across treatment
- e. Proportions of high and low anxiety scores in each group at each time point.

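### The remote-consent route returns the baseline questionnaire on the consultation day, which cannot be squared with randomising after baseline and booking ahead, and no described check places its completion before the arm is disclosed

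*Protocol*

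**What the plan says.** **The general sequence.** Section 6.2.2 states: "After eligibility has been confirmed and written consent obtained, and prior to randomisation, patients will be provided with a baseline questionnaire packet". If the questionnaire cannot be done on the day of consent, the rule is: "This must be completed within 1 week of the CT appointment, either by post or electronically". Section 6.3 continues: "Following completion of baseline information collection, a member of the research team will randomise the participant to one of the two treatment arms". Under section 6.4, "the participant will be informed of which trial arm they have been randomised to", the consultation is booked where required, and the patient is given its time. Section 7.3 places the consultation on the first day of treatment. Table 2 agrees: randomisation is in the baseline column and the consultation in the week 2 column.

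**The remote route.** Section 6.2.1.1 sends the patient home with the information sheet and the baseline questionnaire, and consent is taken by telephone. After that, "the participant will complete the baseline questionnaire and bring with them to their first radiotherapy appointment", with the stated purpose "to maintain required timelines for data collection outlined below". On written consent it says: "The participant will be asked to complete a written Consent form at their next visit".

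**The validity rule.** Section 8.2.2 treats questionnaires completed outside their time frame as missing. For the first time point the only test is "Baseline within 1 week of CT appointment". The STAI scores at the second and third time points are baseline-corrected.

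**The concern.** Section 3.2 accepts that neither patients nor staff can be blinded, and the primary outcome is self-reported anxiety. In that setting a baseline score is protected from the allocation only if it is recorded before the patient learns the arm. The general sequence gives that protection. The remote route does not visibly give it, because the team first holds the form on the day of the consultation.

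The baseline is used to correct both later STAI scores. If some patients answer it already knowing whether they will meet a physicist, their answers may reflect that knowledge, and the correction carries the difference into the comparison between arms. A form whose time of completion was not recorded cannot be sorted out later at analysis, so this has to be settled in the protocol.

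**Working it through.** **1. Order of events.**

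| Step | General route | Remote route |
|---|---|---|
| Consent | Written, before baseline (6.2.2) | Telephone; written form deferred to the next visit (6.2.1.1) |
| Baseline completed | Before randomisation, within one week of CT (6.2.2) | After telephone consent (6.2.1.1) |
| Baseline reaches the team | On the day, by post or electronically (6.2.2) | Handed in at the first radiotherapy appointment (6.2.1.1) |
| Randomisation | After baseline collection (6.3) | No separate rule |
| Disclosure and booking | After allocation, ahead of the consultation (6.3, 6.4) | No separate rule |
| Consultation | First treatment day (7.3) | First treatment day (7.3) |

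Section 3.3 expects about two weeks between consent with baseline and the first treatment.

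**2. The two ways to proceed in the remote route.**

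- *Randomise once the form is in hand.* Randomisation then falls on the first treatment day. The consultation cannot be booked and its time given beforehand, as section 6.4 describes, and Table 2 is not followed.
- *Randomise earlier so that the consultation can be booked.* The team then allocates and discloses without having seen the form. Section 6.2.1.1 describes no check of the completion date, no confirmation call and no reading of the answers over the telephone.

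**3. Whether section 8.2.2 closes the gap.** Its test is the interval from CT. Randomisation and disclosure can fall inside that week, so the test alone does not separate a form completed before disclosure from one completed after it.

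**4. The planned effect, for scale.** Inputs from section 8.1: difference 10, SD 13, two-sided 5%, power 80%.

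n per arm = 2 × (1.960 + 0.842)² × 13² / 10² = 2 × 7.85 × 1.69 = 26.5, rounded up to 27, so 54 in total. Then 54 / 0.90 = 60. The plan's figures reproduce, and this point does not change them.

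**5. Form of the bias.** Let k be the share of each arm that both uses the remote route and completes baseline after disclosure. Let δ be the difference (intervention minus control) that disclosure makes to those patients' baseline scores. If later scores are unaffected, the difference in mean change is shifted by −kδ.

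The documents give neither k nor δ. Purely as assumptions:

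- k = 10%, |δ| = 2 points: 0.10 × 2 = 0.2 points
- k = 20%, |δ| = 5 points: 0.20 × 5 = 1.0 point
- k = 50%, |δ| = 10 points: 0.50 × 10 = 5.0 points

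These stand against a target of 10. The upper end is an extreme, since k counts only patients who depart from the stated order. If the prospect of a consultation reassures, δ is negative and the bias is toward no effect; if it unsettles, the bias favours the intervention.

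**6. Setting doubtful forms aside instead.** If unverified baselines were treated as missing and those patients dropped out of the comparison, power by the normal approximation would fall from 80.7% at 27 per arm to 76.5% at 24.3 (a further 10% lost) and 71.5% at 21.6 (a further 20% lost). These loss rates are also assumptions.

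**The case against.** The strongest reply is that handing in a form is not the same as completing it. Section 6.2.1.1 ties completion to telephone consent and refers to the timelines that follow. Section 6.3, read literally, forbids randomising before baseline collection is complete, so a form filled in after allocation would already breach the protocol. The route is presented as a contingency, and the questionnaire and case report form, which are not shown, may carry a completion date.

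Most of this stands. A reader might infer that the protocol instructs staff to randomise remote patients first; it does not. A reader might also infer that the team could never establish when a form was completed. The documents show only that no check is described.

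Two further inferences should be resisted. The baseline does not correct every outcome: section 8.2.2 states the correction for the STAI at the second and third time points, and none is stated for imaging shifts, surface-guidance data or treatment adherence. Nor is the one-week limit itself an error because it could discard a form completed on day 8 but before randomisation. A fixed window is a legitimate choice that keeps baselines comparable, it applies to all patients, and the handling of missing values may be left to the analysis plan.

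What the reply does not answer is the sequence. The literal rule in section 6.3 and the hand-in on the first treatment day leave no room for the advance booking in section 6.4, so one of them has to give, and nothing says which.

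**Conclusion.** The contradiction holds. As written, the remote route cannot be carried out without either randomising before the baseline form is seen or giving up advance booking of the consultation. The first option permits a baseline completed with knowledge of the arm, and neither section 6.2.1.1 nor section 8.2.2 describes anything that would detect it. The written-consent step has the same ordering problem.

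The quantity exposed is the primary outcome, the STAI at the two post-baseline time points. The size of any bias cannot be derived from the documents. The range of 0.2 to 5.0 points in the working rests wholly on assumed shares and shifts and shows scale only. A reader might take it as evidence that the trial will be biased by some such amount; the documents do not support that. The case for acting is that the gap is avoidable, concerns an unblinded self-reported outcome, and cannot be repaired once the data are in.

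**What to change.** - **Section 6.2.1.1:** replace the hand-in at the first appointment with a requirement that, before randomisation and disclosure, the completed and dated baseline questionnaire is received by post or electronically, as section 6.2.2 already allows, or its answers are recorded by telephone with the date.
- **Section 8.2.2:** add that a valid baseline STAI must be completed before randomisation. Keep the one-week window.
- **Sections 6.2.1.1 and 6.2.2:** reconcile the wording on written consent, so that it is clear whether telephone consent is enough for baseline collection and randomisation.

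**Cost.** A small protocol amendment, with the ethics submission and any re-consent that sections 10.1 and 6.2.1 attach to amendments, plus some chasing of remote patients. The return routes exist and the team already telephones these patients. Answers taken by telephone differ in mode from a self-completed form, but because they are given before allocation the difference cannot depend on the arm; recording the mode is enough.

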6.2.2. Baseline data

After eligibility has been confirmed and written consent obtained, and prior to randomisation, patients will be provided with a baseline questionnaire packet to be completed, and a member of the research team will complete the baseline case report form (CRF).

- Sociodemographic information collected from either medical records or selfreported by the participant.
 - Contact details, and preferred method of contact (to facilitate sending of appointments and questionnaire reminders).
 - o Year of birth
 - o Gender
 - Education level
 - Marital status
 - Employment status
 - Whether the participant deems English to be their 'first' or 'second' language
 - Clinical information collected from medical records
 - Area/site of treatment
 - Number of radiotherapy treatments (fractions) referred.
 - Has the participant had previous radiotherapy?
 - Has the participant been scanned with particular motion management, e.g. deep inspiration breath hold (DIBH)?
- Patient-reported anxiety STAIS6 questionnaire
- Health literacy assessment
- EQ-5D-5L questionnaire
- Information and communication questions
- Technical satisfaction questions

Ideally the participant-reported data will be collected on the day of consent, however it is acknowledged this may not be possible in all cases. This must be completed within 1 week of the CT appointment, either by post or electronically.

